3.2 Study Visits

For each subject, a maximum of 9 scheduled visits will be performed. The procedures and assessments to be performed during each period/time point are indicated in [Table 1](#).

Further relevant details of the evaluations to be performed at each visit are described below.

3.2.1 Screening Period (Day -28 to Day -1)

3.2.1.1 Screening Visit

At Screening, potential subjects will be given a detailed oral presentation describing the nature, purpose, risks, and requirements of the study and will receive detailed written information. Subjects will be given ample time to consider participation and ask questions that will be adequately addressed by site personnel.

Once the subject is satisfied that he/she is willing to participate in the study, he/she will be asked to sign the study informed consent form (ICF) (refer to [Section 11.2.4](#) for further detail regarding the ICF). The Investigational Site personnel obtaining written consent from the subject will also sign the form to confirm consent has been obtained.

Once signed, the Investigator will retain the original ICF for the subject's study records and provide the subject with a signed copy. The Investigator will verify that informed consent has been obtained from each subject prior to enrollment into the study and prior to the subject undergoing any study-related procedures.

Subjects will report to the clinic in the morning following a 10-hour fast. Screening activities after obtaining informed consent will be conducted and consist of the following:

- Review of eligibility criteria.
- Collection of demographic data (sex, date of birth (DOB), race, and ethnicity).
- Completion of medical history, including tobacco and alcohol use.
- Review of prior and concomitant medications and supplements.
- Physical examination will be performed.
- Height and weight will be measured.
- IGA will be performed.
- PASI Score will be evaluated.
- BSA will be measured.
- DLQI questionnaire will be completed.
- Measurement of vital signs (SBP/DBP and heart rate).
- Collection of fasted blood samples for (see [Section 6.3.2](#) for a list of tests):
 - Clinical laboratory tests (including serum pregnancy test for females and activated partial thromboplastin time (aPTT) test).
 - Serology (Hepatitis B and C, and HIV).

- CCTA will be performed.

For subjects who meet eligibility criteria based on the Screening assessments, instruction will be provided on the following:

- Use of adequate contraceptive methods (see [Section 5.10.2](#)) for the duration of the study (Screening through Follow-up Visit (Visit 8));
- Avoid use of concomitant medication unless deemed necessary by the Investigator, and avoid prohibited medications as defined in [Section 5.9.2](#);
- Restraint from excessive alcohol use or binge drinking during the study, and restraint from drinking alcohol for 72 hours prior to all study visits.

3.2.2 Screen Failure

A screen failure is defined as a subject who has signed the ICF, does not meet all the entry criteria outlined in [Section 4](#) of this protocol (note that this criteria includes assessments through Visit 1) and was not randomized to receive the study treatment (active or placebo). The Investigator is responsible for keeping a record of all subjects screened for entry into the study and subsequently excluded. The reason(s) for exclusion will be recorded in the source documents and on the Screening log. Screen failure subjects will have only their consent, demographic and reason for screen failing (including, where applicable, the unmet inclusionary or exclusionary criteria) data entered into the electronic data capture (EDC) system, unless an adverse event was responsible for the subject's screen failure, in which case all electronic case report form (eCRF) data collected for that subject during the Screening process will be entered into the EDC system.

3.2.3 Baseline Period (Day 1)

3.2.3.1 Visit 1 (Week 0, Day 1 ± 1 day)

The morning of randomization (Day 1), subjects will report to the clinic in the morning following a 10-hour fast. The following activities will be performed:

- Review of eligibility criteria. *
- Review of concomitant medications and supplements.
- Physical examination will be performed. *
- Weight will be measured. *
- IGA will be performed. *
- PASI Score will be evaluated. *
- BSA will be measured. *
- DLQI questionnaire will be completed. *
- I-NRS questionnaire will be completed.
- Measurement of vital signs (SBP/DBP and heart rate). *
- Collection of fasted blood and urine samples for (see [Section 6.3.2](#) for a list of tests): *
 - Clinical laboratory tests (including urine pregnancy test for females, aPTT test, and biomarkers test).
 - Immunogenicity testing.
 - PK assessment.

- Subjects will be randomized to receive IV infusion of either orticumab [REDACTED] or placebo.*
- Subjects will receive IV infusion of either orticumab [REDACTED] or placebo and will be monitored for at least 1-hour after the infusion.
- AEs will be recorded.
- Subjects will be instructed to return to the clinic in 1 week for Visit 2.

* Assessments to be performed/samples to be collected prior to dosing.

3.2.3.2 Visit 2 (Week 1, Day 8 ± 1 day)

Subjects will and report to the clinic in the morning following a 10-hour fast where the following activities will be performed:

- Review of eligibility criteria prior to dosing.
- Collection of fasted blood samples prior to dosing for:
 - PK assessment.
 - Biomarker testing.
- Subjects will receive IV infusion of either orticumab [REDACTED] or placebo and will be monitored for at least 1-hour after the infusion.
- Review of concomitant medications and supplements.
- IGA will be performed.
- PASI Score will be evaluated.
- BSA will be measured.
- Measurement of vital signs (SBP/DBP and heart rate).
- AEs will be recorded.
- Subjects will be instructed to return to the clinic in 1 week for Visit 3.

3.2.3.3 Visit 3 (Week 2, Day 15 ± 1 day)

Subjects will report to the clinic in the morning following a 10-hour fast where the following activities will be performed:

- Review of eligibility criteria prior to dosing.
- Collection of fasted blood samples prior to dosing for:
 - PK assessment.
 - Biomarker testing.
- Subjects will receive IV infusion of either orticumab [REDACTED] or placebo and will be monitored for at least 1-hour after the infusion.
- Review of concomitant medications and supplements.
- Measurement of vital signs (SBP/DBP and heart rate).
- AEs will be recorded.
- Subjects will be instructed to return to the clinic in 1 week for Visit 4.

3.2.3.4 Visit 4 (Week 3, Day 22 ± 1 day)

Subjects will report to the clinic in the morning following a 10-hour fast where the following activities will be performed:

- Review of eligibility criteria prior to dosing.
- Collection of fasted blood samples prior to dosing for (see [Section 6.3.2](#) for a list of tests):
 - Clinical laboratory tests (including urine pregnancy test for females, biomarkers test, and aPTT test).
 - Immunogenicity testing.
 - PK assessment.
- Subjects will receive IV infusion of either orticumab [REDACTED] or placebo and will be monitored for at least 1-hour after the infusion.
- Review of concomitant medications and supplements.
- Physical examination will be performed.
- IGA will be performed.
- PASI Score will be evaluated.
- BSA will be measured.
- DLQI questionnaire will be completed.
- I-NRS questionnaire will be completed.
- Measurement of vital signs (SBP/DBP and heart rate).
- Weight will be measured.
- AEs will be recorded.
- Subjects will be instructed to return to the clinic in 4 weeks for Visit 5.

3.2.3.5 Visit 5 (Week 7, Day 50 ± 3 days)

Subjects will report to the clinic in the morning following a 10-hour fast where the following activities will be performed:

- Review of eligibility criteria prior to dosing.
- Collection of fasted blood samples prior to dosing for:
 - PK assessment.
 - Biomarker testing.
- Urine pregnancy test for females prior to dosing.
- Subjects will receive IV infusion of either orticumab [REDACTED] or placebo and will be monitored for at least 1-hour after the infusion.
- Review of concomitant medications and supplements.
- Physical examination will be performed.
- IGA will be performed.
- PASI Score will be evaluated.
- BSA will be measured.
- DLQI questionnaire will be completed.
- Measurement of vital signs (SBP/DBP and heart rate).
- Weight will be measured.

- AEs will be recorded.
- Subjects will be instructed to return to the clinic in 4 weeks for Visit 6.

3.2.3.6 Visit 6 (Week 11, Day 78 ± 3 days)

Subjects will report to the clinic in the morning following a 10-hour fast where the following activities will be performed:

- Review of eligibility criteria prior to dosing.
- Collection of fasted blood samples prior to dosing for:
 - PK assessment.
 - Biomarker testing.
- Urine pregnancy test for females prior to dosing.
- Subjects will receive IV infusion of either orticumab [REDACTED] or placebo and will be monitored for at least 1-hour after the infusion.
- Review of concomitant medications and supplements.
- Physical examination will be performed.
- IGA will be performed.
- PASI Score will be evaluated.
- BSA will be measured.
- DLQI questionnaire will be completed.
- Measurement of vital signs (SBP/DBP and heart rate).
- Measurement of weight.
- AEs will be recorded.
- Subjects will be instructed to return to the clinic in 4 weeks for Visit 7.

3.2.4 End of Study/Early Termination Visit (EOS/ET Visit)

3.2.4.1 Visit 7 (Week 15, Day 106 ± 3 days)/ ET Visit

Subjects will report to the clinic in the morning following a 10-hour fast where the following activities will be performed:

- Collection of fasted blood samples for (see [Section 6.3.2](#) for a list of tests):
 - Clinical laboratory tests (including urine pregnancy test for females, biomarkers test, and aPTT test).
 - Immunogenicity testing.
- Review of concomitant medications and supplements.
- Physical examination will be performed.
- IGA will be performed.
- PASI Score will be evaluated.
- BSA will be measured.
- DLQI questionnaire will be completed.
- I-NRS questionnaire will be completed.
- Measurement of vital signs (SBP/DBP and heart rate).
- Weight will be measured.

- CCTA will be performed.
- AEs will be recorded.
- Subjects will be instructed to return to the clinic in 2 weeks for Follow-up Visit 8 (or discharged from the study if terminated early).

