Orticumab has been tested in humans in 3 clinical studies: two Phase 1 studies and one Phase 2 study. In the first-in-human Phase 1 study, orticumab was administered to 28 healthy volunteers as a single intravenous (IV) infusion at doses of 0.007 to 15 mg/kg or as a single SC injection at 1.25 mg/kg (n=6); in the multiple dose phase of this study, orticumab was administered weekly for 4 weeks via IV infusion at doses of 0.25 to 15 mg/kg or via SC injection at 1.25 mg/kg (n=6).

In the second (bioavailability) Phase 1 study, orticumab was administered as a single dose of 360 mg via IV or subcutaneous (SC) injection to (n=22) healthy volunteers. In both studies, orticumab demonstrated linear pharmacokinetics with a half-life of 2-3 weeks. Orticumab was safe and well tolerated in both studies without any reports of treatment-related serious adverse events (SAEs). Local injection site reactions were observed but were mild in intensity and resolved within a few days to slightly more than 1 week without medical intervention.

In the Phase 2 study, (n=49) subjects with stable atherosclerotic cardiovascular disease were administered orticumab via IV [REDACTED] as a single dose followed by [REDACTED]

████████ weekly for 3 weeks then monthly for 2 months. No SAEs due to study drug were reported. All adverse events (AEs) were mild or moderate in severity, with the most common AEs being dizziness, headache, and gastrointestinal (mainly diarrhea). No anti-therapeutic antibodies (ATAs) to orlicumab were observed during or after treatment. No dose-limiting toxicities, deaths, or pregnancies were reported.

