3 INVESTIGATIONAL PLAN

3.1 Overall Study Design and Plan: Description

This randomized, double-blind study is designed to compare the responses of orticumab [REDACTED] or placebo in subjects with moderate to severe psoriasis. A total of 75 subjects (enrolled in at least 17 study sites) with psoriasis will be randomized in a double-blind fashion to receive either an IV infusion of orticumab or placebo for up to 78 days. Before any study-related procedures are conducted, the subjects will sign a written informed consent. Subjects will be screened (Day -28 to -1) for the study, which will include clinical laboratory evaluations and CCTA. Prior to dosing on study Day 1, Baseline assessments will be performed. During treatment periods, dosing will be performed under supervision at the research center. Subjects will visit the research center on the morning of Days 1, 8, 15, 22, 50, and 78 for a pre-dose blood sample for PK purposes, Day 106 for End of Study assessments, and Day 120 for Follow-up assessments.

Following the Screening Period, participants will be enrolled into one of the two groups: [REDACTED] orticumab or placebo. Subjects will be randomized in a 2:1 ratio, orticumab to placebo and receive up to 11 weeks of treatment.

Planned treatments are weekly for 4 weeks, then monthly IV infusions of [REDACTED] orticumab or placebo. The Internal Safety Review Committee (ISRC) will review the blinded safety data after the first subject completes the first dose (Day 1), the first five subjects complete the first dose (Day 1), and the first ten subjects complete the first dose (Day 1). The IRSC will review all adverse reactions to all administered doses at these times. At the Investigator's discretion, subjects may be eligible for psoriasis rescue medications as discussed in [Section 5.9.4](#).

Stopping criteria ([see Section 12.2](#)) will be utilized in this study based on treatment-emergent AEs (defined as AEs that begin or worsen after the first dose of IP) in determining if infusions in existing and future subjects may continue.

The following efficacy analyses measures will be assessed during the study:

- **Psoriasis Area and Severity Index (PASI)**

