3.2.5 Follow-up (FU) Visit

3.2.5.1 Visit 8 (Week 17, Day 120 \pm 3 days)

A post-treatment Follow-up Visit will occur 14 \pm 3 days after completion of the treatment period. Subjects will report to the clinic in the morning where the following activities will be performed:

- Review of concomitant medications and supplements.
- Physical examination will be performed.
- Urine pregnancy test will be performed.
- Measurement of vital signs (SBP/DBP and heart rate).
- AEs will be recorded.
- Subjects will be discharged from the study.

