[1] For Study Weeks 1-15: Clinic visits should occur within ± 1 days. Follow-up Visit should occur within ± 3 days.

[2] Prior and concomitant medications and supplements will be reviewed at Screening, Early Termination (ET) Visit (if applicable), and Unscheduled (UNS) Visit (if applicable). Concomitant medications and supplements will be reviewed as indicated.

[3] Physical examination will include the following organ or body system assessments: general appearance; eyes; ears, nose, and throat; head and neck; chest and lungs; cardiovascular; abdomen; musculoskeletal; lymphatic; dermatological; neurological; and extremities.

[4] Heart rate and blood pressure.

[5] Serum pregnancy test at Screening, urine pregnancy test at Visits 1, 4, 5, 6, 7, and FU Visit.

[6] See Efficacy Assessment Section under “[Cardiometabolic and Inflammatory Biomarkers](#)”.

[7] Subjects withdrawing prematurely from the trial at any visit will have the ET visit procedures completed.

[\$] Height and weight will be measured at Screening and weight will be measured at Weeks 0, 3, 7, 11, 15, and Unscheduled (UNS) Visit (if applicable).

[#] Clinical lab tests will include hematology, serum chemistry (includes a standard lipid panel), and coagulation parameters (includes an activated partial thromboplastin time (aPTT) test).

[^] AE's will only be collected after dosing on Visit 1 (Week 0).

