7.4 Eliciting and Reporting of Adverse Events

AE monitoring will start immediately following the first dose at Visit 1 and will continue through the Follow-up Visit. Any subject with a possible study treatment-related AE at the Follow-up Visit will be followed until resolution or stabilization of the event. Further, any SAE, whether related or unrelated to study treatment that occurs within 30 days following the last dose of study treatment will be followed until resolution or stabilization of the event. This may require additional clinical assessments and laboratory tests. The follow-up results will be recorded in the subject's source documentation and in the eCRF.

Subjects will be instructed to report all AEs experienced during the study, and subjects will be assessed in clinic for the occurrence of AEs throughout the study. To avoid bias in eliciting AEs, subjects will be asked general, non-leading questions such as "How are you feeling?"

All AEs, including pretreatment and TEAEs, reported by the subject, observed, or otherwise identified by the Investigator or other Investigational Site personnel will be documented.

Medical conditions existing at Screening should be recorded as medical history. New or worsening pre-existing medical conditions or diseases are considered AEs if they arise or worsen after dosing (Visit 1) and should be recorded as AEs.

Surgical procedures themselves are not AEs; they are therapeutic measures for conditions that require surgery. The condition for which the surgery is required is an AE if it occurs or is detected following the first dose of study treatment at Visit 1 through the Follow-up Visit. Conditions leading to planned surgical procedures are not AEs if the condition(s) was (were) known before study treatment. In the latter case, the condition should be reported as medical history.

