7.4.2 Reporting of Serious Adverse Events, Including Death

The Sponsor will adhere to all expedited regulatory reporting requirements as per 21 CFR 312.32.

If an SAE, including death occurs during this study or within 30 days following the last dose of the study treatment, the Investigator must notify the Medical Monitor **within 24 hours** after becoming aware of the event.

Initial notification via the telephone does not replace the need for the Investigator to complete and sign the SAE Form within the time frames outlined in the protocol. This timeframe also applies to additional new information (Follow-up) on previously forwarded SAE reports.

Medical Monitor:

[name]
Safety Office, Integrium, LLC
Office: [contact]
Cellular: [contact]
Email: [contact]

SAE Forms will be provided by the Sponsor or Sponsor designated CRO. If all information is not known at the time of initial reporting, an initial report should still be made. In the event there is a question as to whether the experience is serious, the information should be forwarded to the Medical Monitor for review. The Investigator is responsible for following up on completion of the SAE Form. For all SAEs, the Investigator must pursue and provide information to the study Medical Monitor in accordance with the timeframes for reporting specified above. In general, this will include a description of the AE in enough detail to allow for a complete medical assessment of the case and independent determination of possible causality. Information on other possible causes of the event, such as concomitant medications and illnesses, must be provided. In the case of a subject death, a summary of available autopsy findings must be submitted as soon as possible to the Medical Monitor.

In the event of a medical emergency for an SAE that is unexpected (as defined in [Section 7.7](#)) and possibly related to the study treatment(s) (i.e., an adverse reaction or suspected adverse reaction as defined in [Section 7.4](#)), the Investigator in consultation with the Medical Monitor may request that a blind be broken in instances when the knowledge of the assigned treatment may impact the subjects' medical management.

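### Subjects who terminate early are discharged at the ET visit, so no contact is scheduled to cover the protocol's own 30-day post-dose safety windows

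*Protocol*

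**What the plan says.** Protocol 3.2.4.1 uses one visit for both Week 15 and early termination. Its last instruction is that subjects "return to the clinic in 2 weeks for Follow-up Visit 8 (or discharged from the study if terminated early"). Completers go on to Visit 8 and early terminators do not. Table 1 footnote [7] adds that "Subjects withdrawing prematurely from the trial at any visit will have the ET visit procedures completed". It sets no minimum interval since the last infusion.

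Other sections assume observation beyond that point:

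- Protocol 7.4: "AE monitoring will start immediately following the first dose at Visit 1 and will continue through the Follow-up Visit". No exception is made for early termination. The same section requires SAEs arising up to 30 days after the last dose to be followed.
- Protocol 7.4.2: the 24-hour notification duty applies "If an SAE, including death occurs during this study or within 30 days following the last dose of the study treatment".
- Protocol 7.4.2.1: pregnancies are reportable up to 30 days after study medication is discontinued.
- Protocol 12.2: the first stopping criterion counts possibly drug-caused deaths within 30 days of an administration.

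Three provisions help in part. Section 4.4 requires a subject withdrawn for a suspected treatment-related AE to be followed until that event resolves or stabilises. It also requires efforts to reach anyone who misses a follow-up appointment or contact. Section 3.2.6 allows unscheduled visits at the investigator's judgment.

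**The concern.** The sections cannot all be applied to a subject who leaves early. Monitoring cannot run through a Follow-up Visit that the subject is told not to attend. A 30-day reporting duty with no contact behind it depends on the site happening to learn of an event.

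The partial remedies do not close this gap. Following the event that caused withdrawal does not look for a different, later event. It also does not apply to someone who left by choice, for a protocol violation, for prohibited medication, or for an AE judged unrelated. The effort to reach subjects who miss follow-up presupposes a scheduled follow-up, and after ET there is none. Sections 7.4 and 7.8 extend follow-up for AEs and findings present at the Follow-up Visit, which this group does not have. An unscheduled visit needs someone to know already of a problem.

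What is at stake is capture of the first primary safety endpoint, the number and percent of subjects with at least one TEAE or any SAE (SAP 1.3.4). The TEAE definition in SAP 2.7.1 has a start but no end, and neither document plans an exposure adjustment. How long each subject is observed therefore affects the count.

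**Working it through.** **Inputs.** Infusions are given on the days of the pre-dose samples: "Days 1, 8, 15, 22, 50, and 78 for a pre-dose blood sample for PK purposes" (Protocol 3.1). The later visits are "Day 106 for End of Study assessments, and Day 120 for Follow-up assessments". Visit windows are ±1 day for Visits 1-4 and ±3 days for Visits 5-8 (Protocol 3.2). Table 1 footnote [1] gives ±1 day for all of Weeks 1-15, but this does not change the nominal figures. The limit for comparison is the protocol's own 30 days.

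**The plan's own figure.** Protocol 3.2.5.1 places Visit 8 at 14 ± "3 days after completion of the treatment period". Day 120 − Day 106 = 14 days, so the figure is reproduced when counted from Visit 7.

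**Completers.** The last infusion is on Day 78.

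- To Visit 7: 106 − 78 = 28 days (22 to 34 with windows).
- To Visit 8: 120 − 78 = 42 days (36 to 48 with windows).
- First dose to last contact: 120 − 1 = 119 days.

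Visit 8 always falls beyond day 30, so the 30-day windows are covered.

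**Early terminators.** I assume that ET takes place at the next scheduled visit. Interval = next visit day − day of last dose; shortfall = 30 − interval.

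| Last dose received | Days to ET (with windows) | Short of 30 | Short of 42 | First dose to ET |
|---|---|---|---|---|
| Dose 1, Day 1 | 8 − 1 = 7 (5-9) | 23 | 35 | 7 |
| Dose 2, Day 8 | 15 − 8 = 7 (5-9) | 23 | 35 | 14 |
| Dose 3, Day 15 | 22 − 15 = 7 (5-9) | 23 | 35 | 21 |
| Dose 4, Day 22 | 50 − 22 = 28 (24-32) | 2 | 14 | 49 |
| Dose 5, Day 50 | 78 − 50 = 28 (22-34) | 2 | 14 | 77 |
| Dose 6, Day 78 | 106 − 78 = 28 (22-34) | 2 | 14 | 105 |

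If ET were done on an infusion day after dosing, the interval would be 0 and the shortfall 30 days. Footnote [7] does not rule this out.

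**How early stops arise.** Eligibility is reviewed again before dosing at Visits 2-6, and meeting an exclusion criterion is a listed reason for discontinuation (Protocol 4.4). A subject withdrawn on that review at Visit 2, 3 or 4 is in one of the first three rows.

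**How many.** Protocol 4.1 enrols about 75 so that at least 60 complete: 75 − 60 = 15, and 15/75 = 20%. With equal dropout in both arms (an assumption), the 2:1 ratio gives 10 on orticumab and 5 on placebo. This is an allowance, not a forecast.

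**The case against.** The strongest reply is that the effect on the endpoint is small and that some protection exists. Much of this stands.

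- The endpoint counts subjects with one or more TEAEs. Someone who stops because of a TEAE is already in the numerator, and a shorter window cannot remove that subject. Only subjects who leave without a TEAE, and SAEs that come later, can be missed.
- The large shortfall belongs to the weekly phase. Days 22 to 106 are 84 of the 105 days from Day 1 to Day 106 (80%), and there the nominal shortfall is 2 days.
- A same-day ET may be rare. Section 4.4 speaks of the subject coming back for the ET evaluations, and these include a CCTA.
- Section 4.4 does follow the suspected treatment-related AEs that caused withdrawal. The ET visit includes a pregnancy test, and SAEs that the site hears of within 30 days must be reported.
- AE comparisons are descriptive (Protocol 8.7.1).

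A reader might also infer more than the documents support:

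- *That every stop of treatment ends in discharge.* Section 4.4 provides for temporary interruption and restart, and pregnant subjects are followed to outcome.
- *That this is the group most likely to be harmed.* Section 4.4 lists many reasons for leaving that have nothing to do with safety.
- *That most of the last dose is still circulating a week later.* Section 1.1 says "orticumab demonstrated linear pharmacokinetics with a half-life of 2-3 weeks", but single-exponential decay does not fit the earlier Phase 2 data in section 1.2. A Cmax of 286 ug/mL after the first dose would alone leave 286 × 0.5^(21/14) = 101 to 286 × 0.5^(21/21) = 143 ug/mL on Day 22. The reported mean trough that day is 63.1, after further doses on Days 8 and 15. The half-life alone therefore gives no usable residual fraction.

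None of this removes the conflict between 3.2.4.1 and 7.4, or supplies a contact that looks for new events.

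**Conclusion.** The point holds as an internal conflict and a gap in active ascertainment. Section 3.2.4.1 discharges early terminators at ET, while 7.4 keeps every subject under AE monitoring to the Follow-up Visit. The 30-day windows in 7.4, 7.4.2, 7.4.2.1 and 12.2 have no scheduled contact after ET in this group.

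The shortfall is nominally 23 days after doses 1-3 and 2 days after doses 4-6, on the assumption that ET is at the next scheduled visit. It would be larger if ET came sooner. Up to about 15 of 75 subjects could be affected, and those who leave in the weekly phase are affected most.

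Capture of the primary safety endpoint is unequal for subjects who leave without a prior TEAE and for later SAEs. A reader might conclude that the orticumab TEAE rate is biased downward. That would need more early stops on orticumab, and neither document gives dropout by arm, so the direction is unknown. This is a cheap improvement to safety capture. It does not invalidate the safety comparison.

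**What to change.** Reconcile Protocol 3.2.4.1, Table 1 footnote [7] and section 4.4 with 7.4 and 7.4.2. In 3.2.4.1, replace the clause that discharges early terminators, so that a treated subject who terminates early stays under AE and SAE ascertainment. Discharge should follow a scheduled contact that covers the protocol's existing 30-day limit after the last dose. A telephone call is enough. Footnote [7] and 4.4 should state the same.

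This needs no new time limit and no change to treatment. It does not make observation time equal: a subject who stops after dose 1 would be covered for 30 days, against 119 for a completer. It would mean that the protocol's own windows are actively checked for treated subjects who accept the contact.

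The cost is an amendment and about 15 calls, some of which will be declined.
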